Health
Sydney
Local Health District

PMBC Sleep Program

PROTOCOL NUMBER: VERSION 1.0 (APRIL 2018)

ADMINISTRATIVE INFORMATION

DATA CATEGORY	INFORMATION
Scientific Title	A pilot evaluation of sleep program to improve sleep quality in male psychiatric HDU inpatients
Public Title	PMBC sleep program
Date of Registration	TBC
Primary registry and trial identification number	TBC
Date of Registration in primary registry	TBC
Secondary identification numbers	TBC
Source of monetary or material support	Fully funded by the Sydney Local Health District (\$50,000)
Primary Sponsor	Sydney Local Health District
Contact for public queries	[name] [name], [contact]
Contact for scientific queries	[name] [name], [contact]
Countries of recruitment	Australia
Health condition(s) or problem(s) studied	Inpatient male HDU psychiatric patients of all diagnoses
Intervention(s)	Ward-based initiatives and activity groups
Comparator	Routine male inpatient psychiatric HDU patients' length of stay with and without therapy; previous admissions
Inclusion criteria	Males aged 18+ years. Able to give informed written consent. Literacy in English. Inpatient at PMBC psychiatric Male High Dependency Unit (HDU).
Exclusion criteria	Current substance dependence. Severely unwell such that not able to give consent or tolerating participation in group sessions. Severe cognitive impairment or thought disorder. Not

	proficient in English. Recent transmeridian (>2 time zones) travel (within last 1 month).
Study type	Interventional; Allocation: nonrandomized; Masking: none (open label trial)
Primary Purpose	Pilot Study, Feasibility Study
Date of first enrolment	May 2018
Target sample size	N/A (Pilot study, rolling recruitment)
Recruitment status	Recruitment not yet commenced.
Primary outcomes	Actigraphic changes in sleep duration (Respironics Actigraphy data)
Key secondary outcomes	
Sleep quality (weekly Visual Analogue Scale (VAS) and Pittsburgh Sleep Quality Index measured at start and end of study)
 
Self-report duration
 
Length of stay in HDU
 
Use of as needed (PRN) sedatives for sleep
 
Sleep efficiency (actigraphy)
 
Engagement in group
 
Autonomy
 
Participant satisfaction

Protocol Version:	Version 1.0, April 2018
Revision Chronology	Version 1.0, April 2018: Original.
Protocol Amendment Number	0
Authors	[name] BE(Hons) BCom MBBS, [name] BPsych(Hons), [name] MBBS PhD

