We foresee the duration of the pilot study of approximately 6 months. Recruitment is on a continuous basis; with approximately 4-6 patients recruited at any given time.

Initial recruitment phase is one week, where patients are identified (see recruitment procedures).

Initial recruitment will be 4-6 patients. The patient is recruited for as long as they are an inpatient at the HDU and discontinued at their discharge (or at their request). Subsequent patients are then recruited in the same process to maintain 4-6 patients at any given time in the program for the duration of the pilot study.

PARTICIPANTS

Inclusion Criteria

1. Males 18+ years.
2. Inpatient in psychiatric Male HDU at PMBC
3. Willingness to give informed written consent and willingness to participate to and comply with the study.
4. Literacy in English.

Exclusion Criteria

1. Current substance dependence.
2. Severe cognitive impairment or thought disorder that does not allow participants to consent or follow treatment instructions.
3. Recent time-zone travel (within last 1 month).

STUDY OUTLINE

Interventions

The intervention is an integrated Sleep Program. It comprises of two main components, thrice weekly group sessions and ward environmental initiatives. The overarching aim is to improve sleep through;

1. **Increase daytime activity**, particularly in the morning if possible, with use of the balcony and outdoor areas. It has the ultimate aim of establishing routine. Many patients in a hospital setting experience a lack of activity. For example, patients may spend a lot of time in bed watching TV or napping throughout the day.
2. **Setting regular rhythms** – enhanced light/dark exposure to stabilize circadian rhythms.
3. **Stimulus control and relaxation** – simple breathing techniques, relaxing music through headphones, relaxation on bean bags
4. Encourage patient-driven management through **psychoeducation**, ongoing sleep quality monitoring and feedback, and driving behavioural change in the ward milieu.

The total duration of a patient’s participation in the Program is flexible. However, we consider a 2-week duration as the minimum dose.

Ward environmental initiatives

A number of initiatives are adopted, these are summarised below. They are specific to the participants of the study. Bean bag and visual cues (ward posters) are made available to the participants in their own rooms; while headphones are pre-existing equipment available to all patients in the HDU.

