These sessions are held as a mini picnic with healthy snacks. During these sessions, printouts will be discussed individually with participants, especially with respect to their self-evaluation in their Sleep Diaries. This aims to increase insight and empower the participants to take a proactive role in their management.

As a group, the registrars will give further psychoeducation about sleep, with a focus on sleep hygiene, and addressing specific stimuli which affect sleep.

Wednesday sessions are also repeated in a weekly cycle. Patients in their initial and final weeks of the program will be asked to complete the Pittsburgh Sleep Quality Index, modified to reflect the quality of sleep within one week.

Session 3

Session three are held on Fridays and are repeated on a weekly basis. It is split into two components. Firstly, the morning session is in the form of a breakfast barbeque – which is open to the entire ward to participate. Facilitators of sessions 1 and 2 are able to join. This session is an informal way for participants and clinicians to freely exchange ideas and feedback, as well as to reinforce sleep psychoeducation provided in earlier sessions.

Secondly, there will be a booster session on Friday evenings, which is self-directed by the participants and is optional. It entails participants making use of the ward measures made available to them – to enhance relaxation and stimulus control.

Summary table of sessions

Session	Day and time	Content	Measurement tools	
			Sleep diary	Actigraphy
1	Monday 11:30am – 12pm	
 • Cooking group • Preliminary psychoeducation • Program information and obtaining consent • Providing actigraph watch and diary for participant 	X	X
	Tuesday	Nil active intervention for Day 2 participants complete diary +/- nurse Day8 participants - maintain stimulus control and am light goggles	X	X
2	Wednesday (Pre- session)	
 • Collecting watches + analysing actigraphy 	X	X
	Wednesday 11:30am – 12pm	
 • Outdoor session with snacks • Psychoeducation about • Stimulus Control Therapy, Sleep Hygiene • Present sleep results • Administer PSQI and one-item Sleep Quality measure (start and terminating session only) 		
	Thursday		X	X
3	Friday AM	
 • Outdoors session with bacon and eggs 	X	X

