- 2) A factor found on examination of the device (a deterioration in characteristics or performance)

De-identified Serious Adverse Event Reports will be completed as required throughout the study period and sent the ethic committee.

Early Termination

Possible circumstances for early termination of the study include:

1. Early termination initiated by patient due to side-effects, change-of-mind, intolerability, or the perception that their sleep have improved sufficiently such that they no longer require participation in the program.
2. Loss of capacity to consent due to deterioration or variation in mental state
3. Loss of ability to participate due to deterioration or variation in mental state
4. Medical admission of patient due to an acute medical illness whilst inpatient at PMBC
5. Transfer of patient to a different facility.

The study coordinator will be responsible for correspondence with HREC.

Investigators involved in implementing the Sleep Program clinically, can receive formal notification of termination from the participant by verbal or written form. They may receive notice of termination through a delegate (such as the participant's nurse or medical officer responsible). The investigator will need to formally inform the Study Coordinator in written form.

The Study Coordinator will then be required to document termination in digital study data for this participant – whose data will be separated from overall data pool. Early termination data will be kept for discussion purposes but will be excluded in results and statistical analyses.

The Study Coordinator will be responsible for informing the

(who is responsible for what aspect in the process of terminating the study (informing participants, correspondence to HREC, compiling a final study report, unbinding if applicable)).

BLINDING AND UNBLINDING

- a) Blinding (Masking): This trial is an open-label with no attempt at masking
- b) Emergency unblinding: not applicable

STATISTICAL CONSIDERATIONS

Sample Size or Power Calculation

The pilot study will determine the sample size. Power calculation will be the minimum number of samples required to provide adequate power for the primary outcome. (Actigraphic changes in sleep duration)

Statistical Analysis Plan

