Given the pilot study nature we will describe the sample, and the outcomes using but only use analytical techniques to estimate potential effects using difference of means within person measures in SPSS. The pilot study is unlikely to generate sufficient data points for bivariate or multivariate regression modelling.

DATA SECURITY, STORAGE AND ARCHIVING OF STUDY DOCUMENTS

Data Safety and Storage

There are two forms of data collected in pilot study: digital data, and physical data handwritten on paper forms.

Digital Data

Patient name, MRN and date of birth are linked to a Participant ID number. This is kept on an Excel spreadsheet, which is password protected on a single desktop issued by the Sydney Local Health District. The computer will be kept on-site only, in the secured, staff-only section of PMBC, which is accessible via swipe card only. The patient data spreadsheet can only be accessible within a Sydney LHD premises which has access to the SLHD intranet. Back-up copy of this spreadsheet is kept within the Sydney LHD ICT infrastructure.

De-identified digital data includes all data that are entered digitally, and are only identifiable through Participant ID. This includes any digitised data from physical forms, actigraphy data, aggregate length-of-stay data, and so on. Computers with access to these files that are password-protected and individualised for the investigator.

For security, a complete back-up of the data will be kept on a separate, secure Sydney LHD laptop, and is performed on a daily basis. Periodic data analysis files will also be backed-up and kept. Primary access to the Sydney LHD computing facilities will be through physical access onsite and through the intranet. Security will be enforced through restricted, swipe-card physical access, passwords and different levels will be assigned to groups and individuals.

Physical Data

Physical data includes the following; patient-completed self-assessment forms (PSQI, sleep diary, Visual scales), equipment check-in and check-out equipment logs. These are identifiable to patient with *only* the Participant ID.

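### The final PSQI and one-item sleep rating are timed by HDU discharge, which can flatter a first-to-final change; the actigraphy contrast has no stated time points; and the blanket dismissal of regression does not fit the planned nightly data

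*Protocol*

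**What the plan says.** **End of follow-up.** Protocol, Duration: "The patient is recruited for as long as they are an inpatient at the HDU and discontinued at their discharge", or at the patient's own request. The Interventions section treats two weeks as the minimum dose.

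**Self-report timing.** The Session 2 text places the PSQI in a patient's first and last programme weeks. The Summary table of sessions lists the PSQI and a one-item sleep quality measure on Wednesdays, "start and terminating session only". The Administrative Information table instead lists a "weekly Visual Analogue Scale (VAS"), and the Participant Time Line marks self-report measures at recruitment, weekly and at discharge.

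**Primary outcome.** "Actigraphic changes in sleep duration (Respironics Actigraphy data"). The watch is issued at Session 1 and worn throughout participation. The Participant Time Line marks actigraphy at recruitment and weekly, but not at discharge.

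**Analysis.** The Statistical Analysis Plan section limits effect estimation to within-person differences of means, without naming time points, and adds: "The pilot study is unlikely to generate sufficient data points for bivariate or multivariate regression modelling". Under Early Termination, the data of patients who stop early are kept for discussion but left out of results and analyses.

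**Volume of data.** The pilot is to run about 6 months, with new patients recruited "to maintain 4-6 patients at any given time in the program for the duration of the pilot study". The target sample size is "N/A (Pilot study, rolling recruitment"), and under Sample Size or Power Calculation, "The pilot study will determine the sample size".

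**The concern.** A last measurement taken at discharge falls on a different day for each patient, and leaving a high-dependency unit is plausibly linked to doing better. Sleep varies from week to week. If patients tend to leave after a good week, the last week is a favourably selected week, and last minus first is positive on average even when nothing has changed. Dropping those who deteriorate, are transferred or stop early pushes the same way, since those who remain are mainly those who reached discharge. The Hypotheses section also expects the programme to shorten the stay, so one outcome moves the measurement time of another. A patient who leaves before a Wednesday recognised as the terminating one may have no end PSQI.

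The pilot is meant to supply the effect and variance for sizing the next study. Required sample size is inversely proportional to the squared effect, so an inflated effect leads to an undersized successor.

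The stated reason for not modelling matters because it closes off the analysis that would use a common time window and the partial records of early stoppers.

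**Working it through.** The protocol gives no sample size, power or expected effect, so there is no figure of its own to reproduce.

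**1. Nights available.** Inputs from Duration: 4 to 6 concurrent patients, about 6 months (26 weeks × 7 = 182 nights).

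- Patient-nights = places × nights: 4 × 182 = 728; 6 × 182 = 1,092.
- Less the one-week initial recruitment phase (175 nights): 4 × 175 = 700; 6 × 175 = 1,050.
- At an assumed 70% usable: 0.7 × 728 = 510; 0.7 × 1,092 = 764.

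These are ceilings with every place filled.

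**2. Patients available.** Patients = patient-nights / stay. Stay is not given, so it is assumed:

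| Stay (days) | Patients (4 to 6 places) |
|---|---|
| 14 | 52 to 78 |
| 28 | 26 to 39 |
| 56 | 13 to about 20 |

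For between-patient quantities, effective nights = total / (1 + (m − 1) × ICC), with m nights per patient. At 28 days and assumed ICC 0.3 to 0.7, the extremes are 728 / (1 + 27 × 0.7) = 37 and 1,092 / (1 + 27 × 0.3) = 120.

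So a model with one period term and a participant effect is feasible. At 28 days the first 14 nights alone give 26 × 14 = 364 to 39 × 14 = 546 nights. A multivariable regression with the patient as unit would be thin at stays of 4 to 8 weeks.

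**3. Bias of a last-minus-first change with no programme effect.** All inputs here are assumptions. Weekly sleep in SD units is z(w) = φ z(w−1) + √(1 − φ²) e(w), with SD 60 min and no trend. Discharge is possible from the end of week 2, with logit(probability) = −0.9 + β z(w). The change is 60 × (z(last) − z(first)). Simulating 200,000 patients per setting, φ 0.3 to 0.7:

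| β | Discharge odds per SD, exp(β) | Mean last − first | Mean week 2 − week 1 |
|---|---|---|---|
| 0 | 1.0 | about 0 | about 0 |
| 0.25 | 1.28 | +6 to +9 min | about 0 |
| 0.5 | 1.65 | +12 to +18 min | about 0 |
| 1.0 | 2.72 | +21 to +31 min | about 0 |

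In SD units, β 0.5 to 1.0 gives 12/60 = 0.20 to 31/60 = 0.52. That is the relevant scale for the PSQI, if its link to discharge is of the same strength.

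**4. What a fixed window does not remove.** Add an illustrative natural recovery of 15 min per week, with φ = 0.5 and β = 0.5. Week 2 minus week 1 becomes +15 min with no programme effect. Last minus first becomes about +67 min: mean stay is about 4.4 weeks, so recovery adds 15 × 3.4 = 51, and selection adds about 16.

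**The case against.** **The primary contrast.** A reader might infer that sleep duration itself is to be compared between the first and last weeks. The protocol does not say this. Start and end are fixed only for the PSQI and the one-item rating; for actigraphy the choice is open and could be made in an analysis plan not shown here. This objection stands, and the minutes above apply to actigraphy only if the final week is chosen.

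**The regression sentence.** A reader might also infer that several hundred nights refute it. They do not. Nights are clustered within patients, the count is a ceiling, early stoppers are excluded, and the protocol says only that enough data are unlikely. For patient-level multivariable models that caution is sound. What fails is its reach: it also covers a bivariate model of repeated nights.

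**Unused data.** It would go too far to say that most nightly data are wasted. A difference of means can average many nights, and nightly data also serve the descriptive objective.

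**Missing end values.** The Participant Time Line lists self-report weekly and at discharge, consent timing refers to an expected discharge date, and the protocol never says that the one-item measure is the VAS. The plausible gap is therefore mainly in the PSQI, and the schedule passages conflict rather than plainly omit.

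**The simulation.** Nothing in the protocol says that discharge depends on sleep, and at β = 0 the bias vanishes. Week 2 minus week 1 is 0 by construction, because the series has no trend. Both points stand, and step 4 shows the consequence of the second.

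**Conclusion.** The point holds in limited form and should be addressed. The end PSQI and one-item rating are tied to a discharge-dependent session, other parts of the protocol give a different schedule, and early stoppers are excluded. A first-to-final change is then biased favourably wherever better sleep raises the chance of discharge: about +12 to +31 min on the sleep-duration scale (0.20 to 0.52 SD) for discharge odds of 1.6 to 2.7 per SD, SD 60 min and weekly correlation 0.3 to 0.7; smaller for a weaker link; about 0 for none. The direction rests on that one link, and the size on all the assumptions.

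For actigraphic sleep duration the contrast is undefined, so the bias there is a risk and not a stated feature. The statement that data are too few for regression is unsupported for a simple night-level model (at most 728 to 1,092 clustered nights) and reasonable for patient-level multivariable regression. One might infer that a fixed window would isolate the programme effect. It would not: the comparator in the Administrative Information table concerns length of stay and previous admissions, so sleep has no concurrent control and natural recovery remains in any within-person change.

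**What to change.** 1. Make the main within-person contrast a common window: programme week 1 (the first recorded programme nights) versus nights 8 to 14, the protocol's own two-week minimum. No pre-programme nights are scheduled, so describe this as change within the programme; any effect already present in week 1 will not show.
2. Estimate it with a mixed model of nightly sleep duration in SPSS, with a participant effect, a fixed period term and autocorrelated residuals. Include the recorded nights of early stoppers where consent permits, and amend Early Termination accordingly.
3. Replace the regression sentence with one that keeps the caution for patient-level multivariable models only.
4. Reconcile the self-report schedule across the Administrative Information table, the Summary table of sessions and the Participant Time Line. Give the PSQI and VAS at each Wednesday session, analyse week 2, and show final-week values descriptively.
5. State that the fixed window removes selection through discharge timing but not natural recovery.

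Cost: revised analysis wording, a standard mixed-model procedure and a short weekly form. Effects emerging after day 14 become secondary.

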Research has shown that the sleep-wake cycle is strongly linked to the environment (Czeisler et al. 1980; Rea et al. 2008) and disruptions to this cycle may result in sleep disturbances as well as negative cognitive and psychological consequences (Lane & East, 2008). Hospital environments tend to report low lighting levels which may distort the normal circadian sleep-wake rhythms. Bendetti et al. (2001) assessed an inpatient hospital setting over 2 years and reported an average reduction of 3.67 days in admission in those rooms facing east compared to rooms facing the west. The addition of increased outdoor activities and light glasses in the current study increases exposure to light which can assist in stabilising the circadian rhythm.

Moreover, evidence-based interventions such as cognitive behavioural therapy for insomnia (CBT-I) has shown promising results within clinical settings involving patients with schizophrenia, psychosis and patients in acute care (Freeman et al., 2015; Sheaves et al., 2017).

This study has 2 goals. The first goal is a pilot study of an integrated, ward-based behavioural therapy (the Sleep Program) to improve the quality sleep of psychiatric inpatients in order to determine its effect, variance of effect and feasibility. The second is to describe the characteristic of sleep, activity and light exposure of patients in a high dependency psychiatric unit using wrist actigraphy.

Actigraphy

Wrist actigraphy has been used to measure sleep rhythms for over 25 years (Kripke et al., 1978, Mullaney et al., 1980). Actigraphs are watch like devices generally placed on the wrist to record movement. Most are based on weighted activity (accelerometry) counts in a given epoch of time which detect sleep/wake according to threshold values. Activity data is then processed and analysed by computer software programs and specialized algorithms are used to estimate sleep and activity parameters. The analysis utilises algorithms which have been developed, compared and validated since the original use of actigraphs (Cole et al., 1992, Sadeh et al., 1994, Jean-Louis et al., 2001, Tryon, 2005, Kripke et al., 2010). As actigraphic devices have evolved, so too has the number of channels used to collect additional data streams (light, event markers, subjective scores, and off-wrist capacitance). (Ancoli-Israel et al, 2003)

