In conclusion, scientific research suggests that in the clinical setting, actigraphy is reliable for evaluating sleep patterns in patients with insomnia, for studying the effect of treatments designed to improve sleep, in the diagnosis of circadian rhythm disorders (including shift work), and in evaluating sleep in individuals who are less likely to tolerate PSG, such as inpatient psychiatric patients. While actigraphy has been used in research studies for many years, it is only recently that the methodological issues have been systematically addressed in clinical research and practice. With those issues addressed, the use of actigraphy is now being applied to clinical practice. (Ancoli-Israel et al, 2003).

STUDY OBJECTIVES

Primary Objective

To evaluate the effect of the Sleep Program on duration of admission in HDU (compared to controls) and sleep duration (Actigraphy data), in male psychiatric HDU inpatient participants.

Secondary objectives

1. Sleep quality - improvement in the Pittsburgh Sleep Quality Index
2. Sleep efficiency- percentage time in bed vs percentage time asleep
3. To test the engagement (tolerability and practicality) with a structured Stimulus Control Therapy Program
4. Impact on use of as needed (PRN) hypnotics
5. To describe the characteristic of sleep, activity and light exposure of patients in a high dependency psychiatric unit using wrist actigraphy.

Hypotheses

- We hypothesise that a structured stimulus control program for sleep will shorten duration of admission at psychiatric HDU.
- There will be an improvement in the sleep duration and efficiency
- There will be an improvement in the quality of sleep via a reduction of the self-rated Pittsburgh Sleep Quality Index score, measured at the beginning and end of the study.
- Participants in the Bright Light Study will engage in a structured stimulus control therapy program and it will be well-tolerated.

STUDY DESIGN

Design, Study Groups, Number of Participants

This is a pilot study for a complex intervention and we do not know the effect of variance. We seek to test our methodology, exterminate recruitment and retention rates, feasibility and finally, determine the sample size. We also seek to highlight any issues with acceptability, compliance, and delivery of our interventions.

Number of centres

Single-centre, at [name] Centre, male High Dependency (psychiatric) Unit

Duration

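### The primary objective compares HDU stay with routine patients, but the protocol provides no patient-level stays for them, so the control figure may not be restrictable to men like the participants

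*Protocol*

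**What the plan says.** The Primary Objective in the protocol's Study Objectives section begins "To evaluate the effect of the Sleep Program on duration of admission in HDU (compared to controls) and sleep duration (Actigraphy data". A shorter HDU admission is also the first hypothesis. The Administrative Information table gives the comparator as "Routine male inpatient psychiatric HDU patients' length of stay with and without therapy; previous admissions". It states no calendar period, eligibility filter or matching. The same table lists "Length of stay in HDU" among the key secondary outcomes, and both that table and the Sample Size section name actigraphic sleep duration as the primary outcome.

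The form of the stay data is described once, under Data Safety and Storage, Digital Data, where the de-identified files are said to include "actigraphy data, aggregate length-of-stay data, and so on". The preceding sentence says "De-identified digital data includes all data that are entered digitally, and are only identifiable through Participant ID", and the same section says "Patient name, MRN and date of birth are linked to a Participant ID number". Under Enrolment Procedure, the Participant ID is issued to a man who has consented and met the criteria.

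The Statistical Analysis Plan section names one estimator, a within-person difference of means, and expects too few data points for regression.

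**The concern.** Participants are not a random sample of HDU patients. They must have capacity to consent, be literate in English, have no current substance dependence, and have no severe cognitive impairment or thought disorder that prevents consent or following instructions. Two weeks is the minimum dose, and the consent decision can be deferred only until two weeks before expected discharge. The Early Termination section then removes from the analysis men who stop by choice, lose capacity or the ability to take part, are admitted medically or are transferred.

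The comparator, as written, passes through none of these filters. If it reaches the investigators as a summary figure, no one can apply them afterwards. The difference in stay would then mix the effect of the program with the effect of who was let in and who was kept. This is the comparison that the first hypothesis rests on.

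**Working it through.** The protocol states no mean, spread or median for length of stay, no number of controls and no sample size, so there is no figure of the plan's own to reproduce. The check is a comparison of the relevant sections, followed by an illustration under stated assumptions.

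**1. Is stay known man by man?**
- *Participants:* yes, in substance. Each has an ID tied to the MRN, and the Duration section keeps him in the study until HDU discharge or his own request to stop.
- *Previous admissions of participants:* obtainable by the same link.
- *Routine comparators:* not provided for. They are not described as enrolled, so they receive no ID, and no other section describes individual records for them. The only description that could cover them is the word aggregate.

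**2. Which filters can be matched from a summary control figure?**

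| Filter on participants | Section | Applicable to a summary? | Applicable to patient-level records? |
|---|---|---|---|
| No substance dependence | Exclusion Criteria | Only if the summary was built that way | Yes, where recorded |
| English literacy, consent capacity | Inclusion Criteria; Capacity | As above | Partly, where recorded |
| Two-week minimum | Interventions; Informed Consent Process | As above | Yes, from dates |
| Early terminations removed | Early Termination | As above | Partly (transfer, medical admission) |

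The protocol asks for no such construction.

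**3. Direction.** The two-week minimum selects longer stays among participants and so works against the program. The capacity and thought-disorder criteria may select men who are less ill, which could work for it. The exclusion of early terminations could work either way. The net direction is not determined by the documents.

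**4. Illustration of one filter.** Assume that stays are lognormal with mean m and log-SD s, and that participants have the same distribution cut off below 14 days. Let μ = ln m − s²/2. The mean among stays of at least 14 days is

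m × Φ((μ + s² − ln 14)/s) / Φ((μ − ln 14)/s).

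For m = 20 and s = 0.8: μ = 2.996 − 0.320 = 2.676 and ln 14 = 2.639. The ratio is Φ(0.846)/Φ(0.046) = 0.801/0.518, the restricted mean is 30.9 days, and the shift is 10.9 days.

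| Assumed mean (days) | s = 0.5 | s = 0.8 | s = 1.0 |
|---|---|---|---|
| 15 | +6.4 | +12.3 | +17.2 |
| 20 | +4.5 | +10.9 | +16.3 |
| 30 | +2.1 | +8.6 | +14.6 |

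The only difference in stay that the protocol cites is in the Background: an inpatient study that "reported an average reduction of 3.67 days in admission in those rooms facing east compared to rooms facing the west". Eight of the nine assumed cases exceed 3.67 days. That figure is a contrast between rooms, not an expected effect of this program, and serves only for scale.

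**The case against.** The strongest reply is that one undefined word in a data-security list is being asked to carry a design. The list is open-ended, the sentence before it describes data keyed to individuals, and aggregate might simply mean each man's total stay. Aggregates can also be medians, quantiles or summaries by stratum or month. Previous admissions are a named comparator and fit the within-person estimator, which deals with part of the case-mix problem. Matching, medians and time-to-discharge curves are the kind of detail a separate SAP may hold.

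Much of this stands, and it rules out several readings that a reader might infer:
- *That stays are held only in aggregate.* The protocol does not say so, and participants' own stays are traceable.
- *That only crude means are possible.* The reliance on means comes from the analysis paragraph, and regression is set aside there because of too few data points, not because of the storage format.
- *That the loss is beyond repair.* Nothing in the documents shows that individual hospital stays could not still be extracted.
- *That season biases the comparison by a known amount.* Enrolment from May 2018 for about 6 months, with a rationale built on light, makes season worth controlling. But no control period is stated, and nothing converts daylight into days of stay.

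What the reply does not reach is the routine-patient comparison. Individual traceability stops at the enrolled men, previous admissions do not replace the routine controls, and a SAP cannot restrict a summary to eligible men unless patient-level records were obtained.

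**Conclusion.** The point holds in a limited form. The protocol sets a control comparison of HDU stay in its primary objective, leaves the routine comparator unrestricted, and provides no patient-level stays for it. If the control figure is a summary, the comparison is between selected men and unselected men, and the selection cannot be undone from that figure.

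The size of the bias cannot be derived from the documents. The range of about 2 to 17 days rests on assumed lognormal stays and a 14-day cut-off applied to participants alone. It covers one filter, and others may offset it. The two weeks count from joining the program, so 14 days is a floor for the total stay that a full course implies. The protocol does not say, however, that a man discharged sooner would be dropped. The conclusion also assumes that aggregate covers the routine controls, which is the natural reading but not a stated one.

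This is a cheap improvement worth making before the data request is settled, not a fault that invalidates the pilot. Its weight depends on whether length of stay is primary, on which the objectives and the outcome list disagree.

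**What to change.** 1. Under Digital Data, replace the word aggregate with de-identified patient-level HDU admission and discharge dates, age and diagnosis, for participants and for routine comparators.
2. In the Comparator entry, restrict routine comparators to men who meet those entry criteria found in the records and the same minimum-stay condition as participants, preferably from the same calendar months of earlier years. Willingness and capacity to consent will not be fully recorded, so state this as a remaining limitation.
3. Report median stay or time to HDU discharge descriptively for both groups, alongside any difference of means. Treat covariate adjustment as exploratory at most, consistent with the protocol's own expectation that the data will not support regression.
4. Reconcile the Primary Objective, which includes length of stay, with the outcome list, which makes it a key secondary outcome.

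The cost is one extract from the hospital's admission records, a line in the ethics submission and slightly more privacy handling. Recruitment and participant procedures do not change.
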